4.4 Laboratory Assays

4.4.1 Diagnosis of HIV Infection:

As outlined in the 034 protocol we will utilize commercially available HIV antibody assay kits for HIV screening. To be documented as HIV infected for the purposes of this protocol, eligible subjects must have a current positive HIV antibody test and a negative HIV antibody test result within the prior 6 months. A positive antibody test would be defined as either A) HIV + by two different rapid tests B) HIV+ by two different serum ELISA tests C) HIV+ by one rapid AND one serum ELISA test or D) HIV+ by either a rapid test OR an ELISA AND by one HIV western blot. As outlined above, individuals who are NOT HIV antibody positive, based upon any of the above four criteria, may also be enrolled in this study if they are identified in the pre-antibody seroconversion "window".

4.4.2 HIV-1 Viral Load Testing:

The Pune HPTU site will be expected to perform HIV-1 PCR and viral load (VL) measurements for studies outlined in this protocol, as well as other potential HPTN protocols such as preparedness studies, perinatal studies, and ART protocols requiring VL measurements. The HCL will recommend the use of the Roche Amplicor HIV-1 Monitor[™] Test version 1.5 because of its increased sensitivity and ability to detect non Clade B subtypes of HIV-1 (36). This assay would be recommended for sites interested in screening HIV-1 antibody negative specimens for identification of HIV-1 PCR+ subjects in the "window" period for enrollment in this protocol. This same assay would be utilized on-site for all VL assays for study participants. The HCL virology core will provide training for this HIV-1 PCR assay. This assay contains quality control material in the form of negative, low and high standards that will be used with each assay run. There is also an internal standard control that is assayed with each specimen. NARI will also be required to participate in QA proficiency testing on a quarterly or semi-annual basis through a DAIDS-sponsored Virology Quality Assurance (VQA) program already in place in the US. More detailed information on the viral load assay is provided in Appendix C.

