5.1.3 Primary Endpoints

(a) Median HIV-1 viral load between 6 and 12 months after estimated time of primary infection

(b) ELISPOT measurement of HIV-1 peptide-specific T lymphocytes

(c) HLA-Class I MHC alleles

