6.3 Statistical Considerations and Sample Size Calculations

Based upon assumptions outlined below for each of the two primary objectives, the target samples size for this study is a minimum of 20 subjects with recent HIV-1-infection retained for at least 1 year of follow-up. For both primary objectives, HIV-1 viral set point will be an outcome measure. Subjects will be stratified according to median viral load measured between 6 and 12 months after estimated time of primary infection (See Table 1. viral set point=median VL

of visits 5-8). Based upon this calculation, subjects would be stratified into the following categories: <10000 copies/ml, 10000-75000 copies/ml, >75000 copies/ml.

6.3.1 Primary Objective (a).

Gag-specific ELISPOT Response vs. HIV-1 Viral Set Point.

For the purposes of comparing ELISPOT response to viral load set point, gag-specific ELISPOT responses will be stratified into two categories: Responses recognizing two or fewer HIV-1 gag peptides and those responses recognizing more than two different HIV-1 gag peptides. As outlined in Appendix E, all experiments will be performed in duplicate wells. The IFN- γ -expressing spots will be calculated as the number of spots per 100,000 stimulated PBMCs. Results will be expressed as net peptide-specific IFN- γ spots / 10⁵ PBMC. A positive peptide-specific response (responders) will be defined as a mean of greater than 5 spots above the mean spots of the mock-stimulated PBMC. Study participants will be expected to have multiple ELISPOT assays within the first 12 months of follow-up (See Appendix A).

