This is a descriptive sub-study proposed for HPTN 034. Therefore, it is not expected that we will have sufficient sample size to definitively address the primary endpoint. Never the less, we will undertake the analysis as outlined on our projected sample size of 20-30 individuals. However, we have also projected that data from this sub-study would also be available for combining with similar data from other HPTN protocols in the future. Our subsequent "meta-analysis" will compare HIV-1 viral set point with the recognition of more than two (>2) gag peptides at any time point within 12 months since estimated time of infection. Separate and similar analyses will be performed for recognition of HIV-1 subtype B gag and non-B gag peptides. Additional analyses will determine if other ELISPOT outcome measures, such as consistent recognition of more than 2 gag peptides at multiple time points, also correlate with viral set point. We predict a 30% difference between the groups with respect to the proportion of individuals who elicit a broad immunologic response (defined above). With a sample size of n=39 per arm from multiple HPTN protocols in the future, we will have 80% power to detect a 30% difference (p=0.05).

Percent ELISPOT response to >2 HIV-1 gag peptides			Estimated Sa	mple Size
<10000 RNA	10000-75000 RNA	>75000 RNA	N per arm	Total N
copies/ml	copies/ml	copies/ml		
70%	50%	30%	93	279
80%	50%	20%	39	117
90%	50%	10%	20	60

Sample Size Estimate

6.3.2 Primary Objective (b).

HLA Class I alleles vs. HIV-1 Viral Set Point.

A similar "meta analysis" of data from 034A and other similar sub-studies is anticipated for this objective. The proportion of individuals with specific HLA Class I alleles will be compared with the viral load set point. Using HLA A2 as an example (known to be associated with a frequently measurable immune response to gag peptides), we posit that a higher percentage of individuals with this allele will fall into the low viral set point category. Again, we will have an 80% power to detect a 30% difference in the proportion of individuals with HLA A2 given a sample size of 39 individuals per arm.

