- (8.) Good laboratory technique is essential to the proper performance of the assay.

LIMITATIONS OF PROCEDURE:

(1.) The presence of AmpErase in the AMPLICOR HIV-1 MONITOR Master Mix reduces the risk of amplicon contamination. However, contamination from HIV positive controls and HIV positive clinical specimens can be avoided only by

good laboratory practices and careful adherence to the procedures specified above.

- (2.) Use of this product should be limited to personnel trained in the techniques of PCR.
- (3.) Only the Perkin-Elmer GeneAmp PCR System 9600 or GeneAmp 2400 thermal cyclers can be used with this product.
- (4.) Monitoring the effects of antiretroviral therapy by serial measurements of plasma HIV-1 RNA has only been validated for patients with baselines viral loads >= 25,000 copies/ml.

The performance of the Amplicor HIV-1 Monitor Test has only been validated with HIV subtype B specimens.

Signature of Person Administering Consent

Date

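### 034A bands the quantitative viral set point at two unexplained cut-offs for both primary objectives; a log10 comparison fits the gag hypothesis better and would usually be somewhat more powerful

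*Supplement*

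**What the plan says.** Section 5.1.3 of 034A gives the first primary endpoint as a quantity: "Median HIV-1 viral load between 6 and 12 months after estimated time of primary infection". Section 6.3 adds that "For both primary objectives, HIV-1 viral set point will be an outcome measure" and that "subjects would be stratified into the following categories: <10000 copies/ml, 10000-75000 copies/ml, >75000 copies/ml". No source or reason is given for 10,000 or 75,000.

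- **Objective (a), 6.3.1.** On the other axis, "gag-specific ELISPOT responses will be stratified into two categories": up to two gag peptides, or more than two. The sample-size table lists the percentage of broad responders in each viral-load band, with 93, 39 or 20 people per band.
- **Objective (b), 6.3.2.** "The proportion of individuals with specific HLA Class I alleles will be compared with the viral load set point". That sentence could describe either form of analysis, but the next one settles it: "we posit that a higher percentage of individuals with this allele will fall into the low viral set point category". The same 39 per arm is reused.

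The gag hypothesis in 5.1.1 runs the other way round: people who recognise several gag epitopes early are expected to have a lower set point than those who do not. No analysis of log10 set point is specified for either objective, and no test is named for the banded comparison.

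On the assay, 4.4.2 recommends the Amplicor Monitor version 1.5 "because of its increased sensitivity and ability to detect non Clade B subtypes of HIV-1". The limitations in Appendix C, which is headed for the same version, say "The performance of the Amplicor HIV-1 Monitor Test has only been validated with HIV subtype B specimens".

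**The concern.** Set point is measured as a number for every participant and then reduced to one of three labels. People at 11,000 and 70,000 copies/ml count as the same; people at 9,900 and 10,100 count as different. With 20 to 30 people at Pune there is little information to spare, and the same bands carry into the planned pooled analysis.

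The banded comparison also asks a different question from the hypothesis. It asks what share of each viral-load band responds broadly, whereas the hypothesis asks how far set point differs between response groups. A log10 difference with a confidence interval answers the second directly and combines easily across protocols.

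Fixed copy-number cut-offs further depend on how the assay reads in absolute terms, and the document makes two statements about the assay that do not agree.

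**Working it through.** **1. The plan's own figures.** Formula per band, two-sided 5%, 80% power, no continuity correction, where p̄ is the mean of p1 and p2:

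n = [1.96·√(2p̄(1−p̄)) + 0.8416·√(p1(1−p1) + p2(1−p2))]² / (p1−p2)²

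- 80% v 50%: (1.96×0.6745 + 0.8416×0.6403)² / 0.09 = 3.463/0.09 = 38.5, so 39.
- 70% v 50%: 3.720/0.04 = 93.0, so 93.
- 90% v 50%: 3.101/0.16 = 19.4, so 20.

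All three rows reproduce as comparisons of adjacent bands, so the sizing does rest on the bands. At 034A's own size (20/3 = 6.7 to 30/3 = 10 per band) the 80% v 50% comparison has 20% to 28% power by the normal approximation. That is mainly a matter of small numbers and of leaving out the third band, and the protocol does not claim otherwise.

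**2. Banded against log10, smooth association.** The documents give no viral-load distribution, so these inputs are assumptions:

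- log10 set point normal, mean 4.5, SD 0.8; cut-offs at log10 4.000 and 4.875.
- Gag: P(broad response) = 1/(1 + exp(1.3(x − 4.5))). This gives band shares of about 27/41/32% and broad response of 77/52/25%.
- HLA: allele in 30% of people; carriers lower by 0.8 log10 (n=30) or 0.5 log10 (n=117, the pooled total of 3×39).
- 4,000 datasets per setting, two-sided 5% tests. Type I error is about 5% for all tests.

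| Setting | t-test on log10 | Trend on bands | 3x2 chi-square | Gain over trend | Gain over chi-square |
|---|---|---|---|---|---|
| Gag, n=20 | 50% | 45% | 33% | 5 | 17 |
| Gag, n=30 | 68% | 62% | 49% | 6 | 19 |
| HLA 0.8, n=30 | 66% | 55% | 41% | 11 | 25 |
| HLA 0.5, n=117 | 86% | 77% | 67% | 9 | 19 |

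For gag, a rank test on log10 gives 46% (n=20) and 66% (n=30). Its gains are 1 and 4 points over trend, and 13 and 17 over chi-square. The simulation error of each figure is about 0.8 points, so the 1-point gain is not distinguishable from none. Repeat runs agree to within about 3 points.

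**3. Other smooth settings.** With equal thirds per band (log10 mean 4.44, SD 1.02) and about 80/50/20% response, the t-test has 69% (n=20) and 87% (n=30), against 60% and 79% for trend and 49% and 70% for chi-square. With mean 4.0 or 5.0 and SD 0.8, the smallest band holds only 14% or 11% of people: 0.11×20 ≈ 2 to 0.14×30 ≈ 4.

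**4. Stepped association.** Now let response be constant within each band and change only at the cut-offs.

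| Response by band | n | t-test | Rank | Trend | Chi-square |
|---|---|---|---|---|---|
| 80/50/20% | 20 | 47% | 45% | 54% | 42% |
| 80/50/20% | 30 | 64% | 63% | 73% | 62% |
| 77/52/25% | 30 | 51% | 51% | 60% | 49% |

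The trend test on bands now leads by 7 to 9 points over the t-test. The gag result therefore depends on the shape within bands, which 6.3.1 does not give.

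**5. Assay shift.** Suppose the assay reads every sample low by 0.3 log10 (an assumption). With mean 4.5 and SD 0.8, the share crossing a cut-off is P(4.0<x<4.3) + P(4.875<x<5.175) = (0.401−0.266) + (0.801−0.680) ≈ 0.135 + 0.120 ≈ 0.25. A t-test or rank test on log10 values is unchanged by such a shift. The banded test still compares like with like within Pune; it simply uses different effective cut-offs.

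**The case against.** Four points on the other side carry weight.

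- **The gain depends on the model.** A logistic response linear in normal log10 viral load suits a t-test, and under a step at the cut-offs the trend test wins. This stands for gag. It does not remove the point: a step at exactly 10,000 and 75,000 is a special case for which the documents offer no basis, just as they offer none for the cut-offs.
- **The large gaps are against a chi-square that the protocol never names.** This also stands. Against a trend test the gain is modest. Because no test is named, neither comparator can be ruled out.
- **034A disclaims power.** Section 6.3.1 calls it descriptive and says the sample is not expected to settle the endpoint; 39 per arm belongs to a future pooled analysis. A reader might infer that the sub-study overstates its power, and it does not. It will nevertheless run the outlined analysis on 20 to 30 people.
- **The measured value is kept.** The endpoint remains the median, and 6.3.1 foresees further analyses relating other ELISPOT measures to set point without mentioning bands. A log10 analysis is therefore not excluded; it is only not specified.

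A reader might also infer from Appendix C that the cut-offs are invalid at Pune. The documents do not support that. The appendix speaks of assay validation and not of cut-offs; 4.4.2 points the other way and cites a reference; and subtype C at the site is inferred only from the gag peptides supplied (4.4.5). A constant mis-reading moves people between bands without biasing the comparison within Pune, and one that varied by isolate would harm a log10 analysis too.

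**Conclusion.** The point holds as a modest improvement to the analysis of both primary objectives. A quantitative endpoint is cut at two unexplained values, and the comparison built on the bands is not the one the gag hypothesis states.

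If the association is smooth in log10 viral load (mean 4.5, SD 0.8 assumed), analysing log10 set point gains roughly 3 to 11 points of power over a trend test on bands and about 14 to 25 over a 3x2 chi-square. The rank test for gag at n=20 falls just below both ranges. The HLA gains also rest on an assumed allele frequency and log10 shift. For gag the gain over trend is small and its sign depends on the unknown shape within bands, so it would be wrong to say that banding always costs power here.

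The assay conflict is a separate matter of wording. It affects how copy numbers and band labels are read, and comparability when Pune is pooled with other protocols. It does not by itself invalidate the banded test at Pune.

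**What to change.** - In 034A 6.3.1 and 6.3.2, make the main comparison the difference in log10 set point by gag-response group and by HLA allele: mean difference with 95% CI, a rank test as a check, and stratification by protocol when data are pooled.
- Keep the three bands as a descriptive or secondary display. State where the cut-offs come from, and name the test if one is applied to the bands.
- Reconcile 4.4.2 with the Appendix C limitation, so that the document makes one statement about the assay's performance in non-B virus.

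The cost is rewording. Viral load is already scheduled at every visit in the 034A visit table (Appendix A), so no new data, samples or participants are needed, and the band table can still be shown.

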5.0 EVALUATION OF OUTCOMES

5.1 Primary Outcomes

Following the successful implementation of immunologic (ELISPOT) and virologic (viral load measurements) assays at NARI (See quality control and training details above), this project will collect data to address the two stated primary objectives.

5.1.1. Primary Objective (a).

To compare initial CD8-mediated immune response with HIV-1 viral set point

The initial research hypothesis for this objective, based upon prior US-based studies of individuals infected with HIV-1 subtype B, is that HIV-1-infected individuals with early CD8⁺-mediated recognition of multiple HIV-1-gag epitopes (polyclonal response) will demonstrate a lower HIV-1 viral set point, compared with individuals that do not recognize multiple HIV-1 gag epitopes. A further hypothesis is that this correlation will be demonstrated in recently infected individuals across diverse populations infected with different strains of HIV-1. The primary outcome measures for this analysis will be HIV-1 viral set point, defined as the median viral load between 6 and 12 months after estimated time of primary infection, and quantification of the number of different HIV-1 gag peptides recognized by each individual, as measured in an ELISPOT assay. In cases where positive responses are detected in the initial screen of the ELISPOT assay, additional assays will be performed on stored specimens to determine the phenotype of the responding cell, epitope specificity and MHC restriction. Based upon this initial analysis of gag-responses and upon data from other ongoing studies, we propose to consider expanding this ELISPOT analysis to include assessment of recognition of other HIV-1 antigens, including env, nef and tat.

5.1.2 Primary Objective (b).

To compare host immunologic genetic characteristics with HIV-1 viral set point.

The initial research hypothesis for this objective, based upon prior studies in a few countries demonstrating that certain HLA class I alleles may be associated with a slower disease HIV-1 progression, is that there are specific host genetic characteristics that will be associated with a lower HIV-1 viral set point in individuals from non-North American populations

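### 034A names the number of gag peptides recognised as a primary outcome measure, but the only specified analysis cuts it at more than two, with no reason given

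*Supplement*

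**What the plan says.** All references are to the HPTN 034A sub-study protocol in the Supplement.

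- **Outcome (5.1.1).** Alongside viral set point, the primary outcome measures include "quantification of the number of different HIV-1 gag peptides recognized by each individual". The hypothesis contrasts people with early recognition of multiple gag epitopes with others: "compared with individuals that do not recognize multiple HIV-1 gag epitopes".
- **Analysis (6.3.1).** For the comparison with set point, "gag-specific ELISPOT responses will be stratified into two categories: Responses recognizing two or fewer HIV-1 gag peptides" are one category and responses to more than two the other. No reason for this threshold appears in 6.3 or elsewhere.
- **Set point (6.3).** Median viral load is itself grouped: "<10000 copies/ml, 10000-75000 copies/ml, >75000 copies/ml".
- **Sample (6.3.1).** The sub-study is described as descriptive: "it is not expected that we will have sufficient sample size to definitively address the primary endpoint". Even so, "we will undertake the analysis as outlined on our projected sample size of 20-30 individuals".
- **Power (6.3.1).** The 80% power statement, with 39 per arm, belongs to a later pooled analysis across HPTN protocols.
- **Other measures (6.3.1).** Additional ELISPOT outcome measures are allowed for. The single example, consistent recognition over several time points, uses the same cut.

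**The concern.** The plan asks for a count and then specifies no analysis of it. Someone recognising three peptides is treated like someone recognising many more, and someone recognising none like someone recognising two. Section 1.2 asks whether a broadly cross-reactive response goes with a lower set point, so differences in breadth on either side of the cut could carry information.

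The threshold also fits 5.1.1 imperfectly. A person who recognises exactly two peptides recognises multiple peptides in ordinary usage, yet 6.3.1 places that person in the lower group.

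At stake is precision on primary objective (a) in a very small sample, and a result that hangs on one unexplained threshold.

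**Working it through.** **1. The plan's own sample sizes.** The 6.3.1 table gives 93, 39 and 20 per arm. A two-sided 5% comparison of two proportions between adjacent bands, with 80% power, pooled variance and no continuity correction, is

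n = [1.96·√(2p̄(1−p̄)) + 0.842·√(p₁(1−p₁) + p₂(1−p₂))]² / (p₁−p₂)²

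- 80% v 50%: p̄ = 0.65; (1.322 + 0.539)² / 0.09 = 38.5, so 39.
- 70% v 50%: p̄ = 0.60; (1.358 + 0.571)² / 0.04 = 93.0, so 93.
- 90% v 50%: p̄ = 0.70; (1.270 + 0.491)² / 0.16 = 19.4, so 20.

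All three match, so the table contains no arithmetic error. The question is only the choice of analysis variable.

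**2. Cost of the cut if breadth shifts gradually.**

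Inputs from the plan: the percentages recognising more than two peptides in the low, middle and high set-point bands, and a sample of 20-30.

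Assumptions, because the documents give none of these:
- Counts are negative binomial, with dispersion k = 1, 2, 5 or 1000 (the last is close to Poisson). Means are solved so that P(count > 2) equals the plan's percentages.
- The three bands are of equal size (7 or 10 each).
- The test is a two-sided 5% trend test, z = r·√(N−1), rejecting when |z| > 1.96. Here r is the correlation of band order with either the more-than-two indicator or the rank of the count.

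The set-point bands stay as planned, so any difference comes from the peptide cut alone. Power from 10,000 simulated studies per setting:

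| Planning row | N | Cut at more than two | Rank of count | Difference |
|---|---|---|---|---|
| 80/50/20 | 21 | about 70% | 81-82% | 11-12 points |
| 80/50/20 | 30 | 80-81% | 93-94% | about 13 points |
| 70/50/30 | 30 | 41-43% | 57-61% | 15-18 points |

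For 70/50/30 at N = 21 the difference is about 7-9 points. For 90/50/10 it is about 3 points at N = 21 and 1 at N = 30, where power already exceeds 95%. With no association, rejection rates were 0.039-0.060 for the cut and 0.046-0.050 for the ranks. Unequal bands (4/9/8 and 5/15/10) gave differences of 8-15 points.

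**3. A second gradual model.** A bivariate normal latent model was calibrated to the same three rows, with half of subjects above the cut and N = 20-30. The trend test across bands loses 13-17 points at 80/50/20, 11-15 at 70/50/30 and 1.5-8 at 90/50/10. Across other assumed correlations and shares above the cut, the loss runs from near 0 to more than 25 points.

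**4. A threshold model.** Keep the plan's percentages and the trend test of step 2, but let set point affect only whether a person exceeds two peptides. Assume counts uniform on 0-2 below the cut and on 3-8 above it.

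| Planning row | N | Cut at more than two | Rank of count | Difference |
|---|---|---|---|---|
| 80/50/20 | 21 | 70% | 52% | −18 points |
| 80/50/20 | 30 | 80% | 68% | −12 points |
| 70/50/30 | 30 | 43% | 34% | −9 points |

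Under this model the binary measure is better.

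**The case against.** The strongest reply is that 5.1.1 states a two-group hypothesis, multiple against not multiple, with no dose-response within either group. A gradual model therefore builds in the advantage of the count, and a threshold model reverses it (step 4). This stands as a limit on size and direction: a reader might infer that the cut always costs a fixed number of points, or that it discards the signal itself, and the documents support neither. It does not justify leaving the count unanalysed, because 5.1.1 lists it as an outcome measure and 1.2 frames the question in terms of breadth.

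Other objections also stand in part:

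- **No stated power is missed.** A reader might infer that 034A falls short of its 80% power. That figure belongs to the pooled analysis, and 034A expects its own sample to be insufficient. The issue is lost information in an analysis that will still be carried out.
- **The trend test is not the plan's.** 6.3.1 names no test. By the adjacent-band method that reproduces its table, 80% v 50% has about 20% power at 7 per band and 28% at 10. The trend-test figures compare two ways of using the data and are not the plan's own power.
- **Other ELISPOT measures are allowed for.** This is true, but none that is specified uses the count.
- **The count is not yet one number per person.** 6.3.1 expects several assays in the first 12 months, and 4.2 adds monthly visits for people infected within the previous three months. A maximum or cumulative count would rise with the number of assays. In addition, 4.4.5 describes pools of overlapping peptides, and 5.1.1 sends positive screens to further assays for epitope specificity. It should not be assumed that the first screen alone yields a clean count. The fix has to deal with this.

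**Conclusion.** The point holds in a limited form. The count is a primary outcome measure, the cut at more than two has no stated reason, and no specified analysis uses the count.

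If breadth shifts gradually with set point, the cut costs about 8-18 points of power at N = 21-30 under the 70/50/30 and 80/50/20 rows, and about 1-3 under 90/50/10. This rests on negative binomial counts matched to the plan's percentages, equal bands and a trend test. If set point acts only through exceeding two peptides, the cut is the better measure. The documents give no count distribution and cannot settle which applies. That supports adding an analysis of the count; it does not support replacing the binary comparison.

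**What to change.** In 034A section 6.3.1:

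1. Add, as a specified analysis for primary objective (a), a rank analysis of the number of distinct gag peptides recognised: Spearman correlation with set point, or a Jonckheere trend test across the three bands. Report a confidence interval.
2. Define one count per person that does not depend on how many assays the person had, for example from the first assay or from a visit common to all. State how peptide-pool results become a count of distinct peptides.
3. Keep the comparison of more than two with two or fewer for the pooled analysis and the sample-size table. Give the reason for the threshold and reconcile it with the wording on multiple epitopes in 5.1.1.

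The cost is a few sentences and one more analysis of an outcome that 5.1.1 already requires. The sample-size table stays expressed in the binary measure.

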The proportion of individuals with certain HLA Class I alleles will be compared between infected and uninfected individuals. Using HLA A2 as an example (known to exhibit good immune response to gag), we posit that a higher percentage of this allele will be found in the uninfected cohort. Using a similar calculation to 6.3.1, we will have 80% power to detect at least a 25% difference in allelic frequency between the two groups.

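### The HLA primary objectives of 034A and 034B compare several unnamed class I alleles with no multiplicity control, while the stated 80% power covers one unadjusted comparison

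*Supplement*

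**What the plan says.** HLA class I is a primary endpoint in both laboratory sub-studies (5.1.3 in each), listed as the whole class and not as particular alleles.

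- **034A hypothesis (5.1.2):** "there are specific host genetic characteristics that will be associated with a lower HIV-1 viral set point in individuals from non-North American populations". 034B 5.1.2 has the same form, with lower risk of infection as the outcome.
- **034A analysis (6.3.2):** "The proportion of individuals with specific HLA Class I alleles will be compared with the viral load set point". HLA A2 is brought in as an example, expected to be more common in the low set-point band, and the section claims "80% power to detect a 30% difference in the proportion of individuals with HLA A2 given a sample size of 39 individuals per arm".
- **034B analysis (6.3.2):** "The proportion of individuals with certain HLA Class I alleles will be compared between infected and uninfected individuals". A2 is again the example. The section claims 80% power for a difference of at least 25 points in allelic frequency, by a calculation like that of its 6.3.1.

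Neither sub-study lists the alleles, says how many will be tested, designates one as primary, or mentions adjustment. Both say in 5.1.2 that the analysis may be widened to HLA class II and co-receptor genotypes in the light of the first results. The only significance level, 0.05, is in the ELISPOT power sentence of 034A 6.3.1; 6.3.2 takes it over by reference. 034B gives none.

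**The concern.** The hypothesis is that some class I characteristics are associated with the outcome, without saying which. Any allele could therefore be offered as support. If several alleles are each compared at 0.05, the chance that at least one differs by luck grows with their number, and nothing in either section limits the number or corrects for it.

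The power statement is worked out for a single allele at an unadjusted level. Without correction, the error rate for the objective is well above 0.05. With correction, the 80% no longer holds for any one allele. So the stated level and the stated power do not describe the same analysis, and this is a primary objective in both sub-studies.

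**Working it through.** **Inputs.** From 034A 6.3: 39 per arm, 80% power, a 30-point difference, p=0.05. The table in 6.3.1 gives 80%, 50% and 20% across the three set-point bands in the row with 39 per arm. The number of alleles, k, is not in the documents and is varied here.

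**1. Reproduce the stated size.** With p1 = 0.80, p2 = 0.50 and mean 0.65:

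n = [1.960·√(2·0.65·0.35) + 0.842·√(0.80·0.20 + 0.50·0.50)]² / 0.30² = [1.960·0.6745 + 0.842·0.6403]² / 0.09 = 38.5, so 39.

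Power at 39 = Φ[(0.30·√39 − 1.960·0.6745)/0.6403] = Φ(0.861) = 80.5%.

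The other rows agree (70 v 50% gives 93; 90 v 50% gives 20). A one-sided test would give 31 and a continuity correction 45, so the plan's figure is one comparison at two-sided 0.05 without adjustment.

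**2. Power per allele if corrected.** Replace 1.960 by the normal quantile for 0.05/k (Bonferroni). For k = 10 the quantile is 2.807, and Φ[(1.8735 − 2.807·0.6745)/0.6403] = Φ(−0.031) = 48.8%.

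**3. False positives if not corrected.** With k independent tests and no true association:

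- any difference, either direction: 1 − 0.95^k
- a difference in the protective direction only: 1 − 0.975^k, because half of the two-sided 0.05 lies on that side.

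| k | Bonferroni power per allele | n per arm for 80% power | Any false difference | False protective allele |
|---|---|---|---|---|
| 1 | 80.5% | 39 | 5% | 2.5% |
| 5 | 58% | 58 | 23% | 12% |
| 10 | 49% | 66 | 40% | 22% |
| 14 | 44% | 70 | 51% | 30% |
| 20 | 40% | 74 | 64% | 40% |
| 28 | 36% | 78 | 76% | 51% |

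At 27 alleles the last column is 49.5%.

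**4. Sensitivity to the assumptions.**

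- *Dependence.* Simulated carrier status at 39 v 39, with the alleles of a locus competing, gave 52-55% (any) and 32-34% (protective) for 14 alleles at one or two loci, and about 78% and 56% for 28-30 alleles. Linkage between loci was not simulated and would lower the figures somewhat.
- *Choice of test.* The plan names none. With Fisher's exact test and carriage spread over 5-40%, the figures fall to 28% and 15% (k = 14), 38% and 21% (k = 20), and 51% and 30% (k = 30).
- *Contrasts.* Three set-point bands allow more than one contrast per allele. The table assumes one; more would raise the error.
- *Baseline.* The 80 v 50% is borrowed from the ELISPOT table. For other carriage levels, power for a 30-point difference at 39 per arm runs from 76.5% to about 93%.

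034B is not put through step 2, because its 6.3.2 gives neither a baseline frequency nor a significance level. Step 3 applies to it unchanged if 0.05 is used.

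**The case against.** **No decision rule is stated.** A reader might infer that an association will be declared if any class I allele reaches p=0.05. No section says so. The alleles are called specific in one sub-study and certain in the other, which fits a short candidate list as well as a full scan. This stands: the gap is that the plan leaves such a reading open, not that it adopts it.

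**The size depends on an assumed count and direction.** A reader might also conclude that 14 alleles suffice for a false protective finding more often than not. They do not. Fourteen is the crossing point for a difference in either direction; in the protective direction it gives about 30%, and 28 alleles are needed to pass 50%. With Fisher's test the figures are lower still.

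**034A is modest about itself.** It calls itself descriptive, expects 20-30 subjects, does not claim a definitive answer, and places the 39 per arm in a future pooled analysis. That stands for the sub-study's own data. But 6.3.2 states the level of power for that pooled analysis and says nothing about how many alleles it will test. The statistical section of 034B has no such disclaimer.

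**A single primary allele narrows the objective.** Making A2 the only primary comparison would turn a sizing example into the hypothesis, and the documents do not compel it. This also stands, so the fix below offers an alternative.

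**Conclusion.** The concern holds in a limited form. Both sub-studies plan to compare several unspecified class I alleles for a primary objective that any of them could meet, without multiplicity control, and the 80% power in 034A is correct only for one allele at unadjusted two-sided 0.05.

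The size depends on a number the documents do not give. For 5 to 20 independent alleles, the chance of some false difference is 23% to 64%, and of a false protective allele 12% to 40%. Correcting by Bonferroni leaves 58% to 40% power per allele at 39 per arm. These figures assume independence, one contrast per allele and nominal test size.

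The documents do not support saying that a positive result would be worthless or that the plan's rule usually fires by chance, since they contain no such rule. In 034A the point bears on the planned pooled analysis; in 034B it bears on the stated analysis directly. It is worth correcting but does not threaten the sub-studies.

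**What to change.** In 034A 6.3.2 and 034B 6.3.2, choose one of two routes:

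1. Name in advance the allele, or short list of alleles, for the primary comparison, with adjustment if there is more than one. HLA A2 is the natural candidate, since both sections already use it for sizing and give a reason and a direction for it.
2. Test the class I alleles as one family, with Holm or permutation max-statistic adjusted p-values.

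Under either route, report all other alleles as hypothesis-generating, and state that the 80% power covers a single pre-named allele at unadjusted 0.05. In 034A, say that the rule applies to the pooled analysis.

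The cost is a few sentences and a routine adjustment, with no extra subjects or assays. The downside is less power to call other alleles confirmed; they can still be reported as leads.
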